The same analyses were applied to the measures obtained at follow-up. Overall, the finding from the follow-up session suggest that the 'signal' detected in the test session had substantially dissipated. However, there were a number of observations that bear mention. First, the mean craving difference score of the propranolol treated individuals (\bar{x} = -32.0) trended towards being lower than that of the placebo treated individuals (\bar{x} = -21.3; $t > 1.4$, $p < .08$). Second, although not powered to detect differences in cocaine use, we preliminarily examined group differences on cocaine use status (self-report abstinence or use) at follow-up. Self-report data indicated that 43% of the propranolol group and 35% of the placebo group participants reported using cocaine, a difference that was not significant, $\chi^2(1) < 1$, $p = .57$. Given the possibility that amount of cocaine use may have differed between groups, we computed a difference score consisting of the participants mean dollar amount of cocaine used during the follow-up period (\bar{x} days = 9.0) minus their mean dollar amount of cocaine used during an equivalent number of days prior to study participation. The mean reduction, from pre-study levels, in dollar amount of cocaine used by the propranolol and placebo groups of \$337 and \$228, respectively, a difference that did not exceed statistical threshold, $t(41) < 1$, $p = .23$.

Since the difference scores indicate the magnitude of craving decrement from session 1 to session 2 was greater for propranolol-treated participants, the depicted findings are consistent with the hypothesis that pharmacological blockade of adrenergic activity after retrieval/reactivation of memories that support craving should disrupt memory reconsolidation and subsequently dampen craving and cue reactivity to the cocaine cues. The findings on the HR and BP measures are also consistent with the reconsolidation disruption hypothesis. Overall, the study findings are consistent with several basic neuroscience studies⁴¹⁻⁴³ documenting disruption of memories for learning previously established via cocaine reinforcement.

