The primary goal of **Phase 2** will be to assess the effects of post-retrieval propranolol on indices of cocaine use obtained over a 6-week follow-up in which abstinence is no longer reinforced. Drug use will be retrospectively evaluated during weekly interviews using a calendar-based assessment and urine drug screens will be performed 3 times each week to provide an objective assessment of drug use/abstinence. At week 1, 3 and 6, laboratory-based test/follow-up CCE sessions (similar to identical to the test CCE session in Phase 1) will permit (a) continued assessment of the maintenance of treatment effects on craving and cue reactivity to cocaine cues, and (b) assessment of generalization of DoR effects to novel cocaine picture cues (detailed below in the procedure section).

B. Participants

A total of 180 non-treatment seeking, cocaine-dependent men and women (60 per treatment group), aged 18 or older, will be tested over a 54-month period (see Alternative Design Considerations section for a rationale pertaining to recruitment of non-treatment seekers). However, after getting close to the end of our recruitment we have found that 180 is not enough to collect the number of completers we need. We have increased enrollment to 200 in hopes to collect the number of completers we need to have significant power for statistical tests. This increase enrollment to approximately 67 per treatment group. Inclusion/exclusion criteria are detailed in the Protection of Human Subjects portion of this application.

Sample Size Estimation

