As in the R21, urn randomization will be used in assigning participants to the two propranolol groups (40PP & 80PP) and the placebo group (PBO)⁶⁸ while balancing treatment assignment on two variables. To maximize the power for a comparison of effect across gender and minimize confounding, gender will be balanced during the randomization. Dollar amount of cocaine use at baseline (pre-study involvement) is a likely prognostic factor on craving and other outcome measure and will be controlled during randomization. Specifically, the total dollar amount of cocaine use in the 3 months prior to study involvement will be determined (using the Timeline Follow-Back) and the following binary urn variable will be used: Participants with \leq \$1000.00 cocaine use pre-study involvement vs. participants with $>$ \$1000.00 cocaine use pre-study involvement. The effects of additional factors such as age and duration of use will be statistically controlled during the analysis (if necessary, see Data Analysis Plan below) since further stratification of the randomization could yield some stratum with very small expected sample sizes. This could lead to significant imbalance in the overall study.

Medication Administration

Immediately following the completion of the cue exposures in each of the first two retrieval CCE sessions (described below), one of three medications will be administered in accordance with randomization; 40 mg of immediate-release propranolol, 80 mg of immediate-release propranolol or a matching placebo will be administered. Medications will be compounded, packaged and dispensed by the MUSC Investigational Drug Service (IDS), who will also oversee the randomization procedures for the study and record the treatment assignment. The IDS provides 24-hour, seven-days-a-week, on-call availability to randomize, enroll, dispense medications and unblind as necessary.

D. Phase 1 Laboratory Session Procedures

Verification of Abstinence

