The main cue reactivity outcome measures for the Phase 1 are subjective craving and physiological reactivity. Summary mean and peak values for craving (and related subjective measures) will be computed for all CCE sessions administered over the course of the study (i.e., all retrieval and test/follow-up sessions). Outcomes for the physiological measures (heart rate, skin conductance and blood pressure) will be computed in a similar fashion. However, data reduction on the HR and SC measures will precede computation of the summary values. The main cocaine use outcomes in Phase 2 will be (1) latency (days) to first use, (2) number of cocaine using days during follow-up, (3) dollar amount of cocaine used during follow-up, and (4) proportion of positive vs. negative UDS. Summary values on outcome measures obtained during the first retrieval CCE session (i.e., before any medication is administered) will serve as baseline (cue-elicited) outcomes and will be used as covariates in the data analytic plan described below.

Data Analysis Plan

Baseline demographic and clinical measures will be compared across treatment groups using standard statistical methods. Categorical demographic/clinical variables will be analyzed using Pearson chi square tests of independence while continuous demographic/clinical variables will be compared using one-way ANOVA procedures.

Phase 1. The first component of hypothesis 1 is that participants receiving propranolol (40 mg and 80 mg) compared to placebo treated controls, will evidence significantly lower cocaine craving and physiological reactivity (HR, SBP, DBP) during the first test/follow-up CCE session. To test this a priori hypothesis, a generalized linear mixed effects model will be developed using model-based estimates to construct group level contrasts (40PP & 80PP combined vs. PBO). A separate contrast will be developed to test the second component of hypothesis 1 that relative to the group 40PP, the group 80PP will evidence lower levels of craving and cue reactivity. Since the expected response pattern characterized in both components of hypothesis 1 is expected to occur to the novel picture cues presented at the end of the test session, a similar analytic plan will be adopted to evaluate the secondary hypothesis.

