Phase 2. The hypothesis (2) that propranolol treated individuals (40PP and 80PP combined), as compared to placebo treated controls, will evidence less cocaine use during the 6-week follow up will be assessed across a limited set of outcomes. Analysis of variance models will be used to assess the continuous outcomes such as the mean number of days reported using and dollar amount spent on cocaine during the follow up. The overall proportion of participants relapsing to cocaine usage will be assessed using logistic regression models to test if differences exist between the propranolol and placebo treated participants at the end of the follow up period. To test the latency to return to cocaine use, Cox proportional hazards regression models will be used to assess both time to first positive UDS/self reported cocaine use as well as time to second positive UDS/self reported use.

In order to fully utilize the longitudinal data, additional analysis will test the pattern of positive UDS data over the entire course of the follow up (measured 3 x weekly for 6 weeks). These models will be developed through the use of generalized linear mixed effects models.^{80,81} To test the hypothesis (3) that participants treated with propranolol (40PP and 80PP) vs. placebo will evidence less craving and cue reactivity to both familiar and novel cocaine cues presented during test/follow-up CCE sessions, linear mixed effects models will be developed. The models will explore the effects of treatment, time, cocaine use status, and the interactions of the factors on the craving and physiologic responses to cocaine cues presented during the week 1, 3 and 6 test/follow up CCE sessions.

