Secondary Analysis. There are a number of secondary analyses of interest. First, it is possible that propranolol will begin affecting craving and cue reactivity as early as the second retrieval session. Therefore, we will use a linear mixed effects model to identify between group differences that develop in the second retrieval session. Second, it is expected that propranolol's ability to disrupt reconsolidation will be related to its bioavailability, which we will index using the plasma sample obtained approximately 90 min after each medication administration. We plan to use regression analyses to assess whether plasma concentrations of propranolol predict variation in the outcome measures (e.g., craving, cue reactivity and cocaine use) obtained across the test/follow-up CCE. Third, we plan to evaluate whether treatment impacts ambient or background craving and cue reactivity^{82,83} (i.e., non-cue-elicited outcomes obtained a half hour before each test/follow-up CCE session) using linear mixed effects models. The models will also test the effects of time and cocaine use status. Fourth, since there is some evidence of gender differences in propranolol metabolism^{84,85} and adrenergic functioning in emotional memory^{86,87}, we will examine associations between gender and treatment outcome. Fifth, we plan to evaluate the effectiveness of the participant blind. Specifically, responses obtained from the participants about which medication group (propranolol dose vs. placebo) they thought they were in will be contrasted with the medication condition to which they were randomized and analyzed via a Pearson chi square test of independence.

Missing Data. Since data for all medicated retrieval CCE sessions in Phase 1 will be collected while the participants are residing at the CTTC, missing data or study dropouts are not anticipated. Inevitably, over the 6-week follow up period, missing cue reactivity and cocaine use data will occur. The missing observations might be 'unit missing', which occurs when a participant does not present at one or more of the time points. The unit missing will be treated as though they are missing (completely) at random. Methods such as multiple imputations⁸⁸ using PROC MI and PROC MIANALYZE will be considered. With respect to the UDS data we will also perform a sensitivity analysis by treating any missing UDS as positive and reanalyzing the data.

I. Alternative Design Considerations and Potential Study Limitations

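### Cheap improvement: the Phase 2 cocaine-use models name no pre-study cocaine use or urn term, although both are already on file for every participant

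*Combined protocol and SAP*

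**What the plan says.** Section 3.H, Data Analysis Plan, Phase 2, sets out the cocaine-use analyses. "Analysis of variance models will be used to assess the continuous outcomes such as the mean number of days reported using" covers using days and dollars. Logistic regression covers relapse, Cox regression covers time to first and second use, and a generalized linear mixed model covers the thrice-weekly urine screens. No covariate is named in any of these.

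Other sections bear on the point:

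- **Section 3.C, General Assessment.** The Timeline Follow-Back records frequency and dollar amount of use for the three months before the study. The same instrument is used at follow-up.
- **Section 3.C, Randomization.** The urn balances gender and pre-study dollars (at most $1000 versus more). It says "Dollar amount of cocaine use at baseline (pre-study involvement) is a likely prognostic factor on craving and other outcome measure".
- **Section 3.H, Outcome Measures.** Summary values from the first retrieval session "will serve as baseline (cue-elicited) outcomes and will be used as covariates in the data analytic plan described below".
- **Section 3.H, Secondary Analysis.** On gender: "we will examine associations between gender and treatment outcome".
- **Section 1.C, R21 results.** The earlier study did use a pre-study baseline for dollars. It took follow-up dollars "minus their mean dollar amount of cocaine used during an equivalent number of days prior to study participation".

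**The concern.** The plan identifies a variable it expects to be prognostic, collects it, and balances the arms on it. It then does not name it in the models for the outcomes to which it most directly relates. The covariate sentence under Outcome Measures does not fill the gap. It supplies craving and physiological responses from a cue session, and these are not pre-study values of using days, dollars, relapse or latency. The cue-reactivity outcomes therefore have a natural baseline covariate, while cocaine use, the primary goal of Phase 2, has none.

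Two things are at stake. The first is precision: if pre-study use predicts follow-up use, an unadjusted comparison leaves explainable variance in the error term, and the Phase 2 power statement has almost no margin above 80%. The second is pre-specification: the plan neither requires nor excludes adjustment, so the choice of covariates stays open until after the data are seen.

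**Working it through.** **Inputs** (section 3.B, Sample Size Estimation, Phase 2): difference 5.6 percentage points of using days, SD 11.3, 96 propranolol versus 48 placebo, alpha .05. Sidedness is not stated. A one-sided test would give 87.7% power and a two-sided test about 80%, so the plan's figure is two-sided.

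**Step 1. Reproduce the plan's figure.** SE = 11.3 × √(1/48 + 1/96) = 1.998. Noncentrality = 5.6 / 1.998 = 2.803 on 144 − 2 = 142 df. Power is 79.5% (80.05% by the normal approximation). The detectable difference at 80% power is 5.63 points. The stated 80% is confirmed as an unadjusted calculation on the raw SD.

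**Step 2. Adjust for three covariates** (pre-study percent using days, gender, $1000 factor). Let r be the within-arm correlation of the outcome with the covariates taken together. The documents give no value, so r is an **assumption** and a range is shown.

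- Residual SD = 11.3 × √(1 − r²).
- Residual df = 142 − 3 = 139.
- Expected variance cost of chance covariate imbalance = (N − 3)/(N − k − 3) = 141/138, with N = 144 and k = 3.
- Adjusted SE = 1.998 × √[(1 − r²) × 141/138].

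For r = 0.3: 0.91 × 141/138 = 0.930, with square root 0.964. SE = 1.926, noncentrality = 5.6 / 1.926 = 2.907, power 82.3%.

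| Analysis | SE | Noncentrality | Power for 5.6 points | Detectable difference |
|---|---|---|---|---|
| Unadjusted | 1.998 | 2.803 | 79.5% | 5.63 |
| Adjusted, r = 0 | 2.019 | 2.773 | 78.6% | 5.70 |
| r = 0.1 | 2.009 | 2.787 | 79.0% | 5.67 |
| r = 0.15 | 1.996 | 2.805 | 79.6% | 5.63 |
| r = 0.2 | 1.978 | 2.831 | 80.3% | 5.58 |
| r = 0.3 | 1.926 | 2.907 | 82.3% | 5.43 |
| r = 0.5 | 1.749 | 3.202 | 88.9% | 4.93 |

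The cost at r = 0 is 79.5 − 78.6 = 0.9 point. The gains at r = 0.2, 0.3 and 0.5 are 0.8, 2.8 and 9.4 points.

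**Step 3. Check by simulation with an urn.** Each row has 10,000 trials with 180 randomised and 20% random loss. Further assumptions: 35% women, the $1000 cut at the median, dollars correlating 0.7 with using days, and a normal outcome. Here r is the correlation with pre-study days. Monte Carlo SE is about 0.4 point.

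| r | Unadjusted | Adjusted |
|---|---|---|
| 0 | 79.3% | 78.2% |
| 0.2 | 78.8% | 79.1% |
| 0.3 | 79.5% | 82.1% |
| 0.5 | 79.4% | 88.6% |

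Type I error at r = 0 and 0.3 was 5.0% and 5.2% unadjusted, and 5.1% and 5.1% adjusted.

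**Step 4. Why not the R21 difference score.** With equal SDs its variance is 2σ²(1 − r). This exceeds the unadjusted σ² whenever r is below 0.5. ANCOVA's σ²(1 − r²) never exceeds σ² apart from the small cost in Step 2.

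**The case against.** The strongest case against is that nothing is broken. The unadjusted tests are valid, the power figure is right, and the plan does not forbid covariates. The gain depends on an r that no document gives, and a low value is plausible: section 3.I reports that 60-65% of the R21 sample had no use at one week and that dollars fell 85% from pre-study levels. The plan calls dollars prognostic but never says so of using days. At r = 0.2 the simulated gain of 0.3 point is within Monte Carlo error. Gains were computed for using days only. All of this stands. It limits the size of the point and rules out calling the change free. It does not show that leaving the covariates unnamed is the better choice.

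A reader might infer three stronger criticisms. The documents support none of them.

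- **That the plan adjusts only when a baseline test shows imbalance.** The Randomization section says certain factors "will be statistically controlled during the analysis (if necessary, see Data Analysis Plan below", and the Data Analysis Plan opens with "Baseline demographic and clinical measures will be compared across treatment groups using standard statistical methods". But the first sentence concerns additional factors such as age and duration of use, not the urn variables or pre-study use. Nothing says that the baseline tests decide adjustment.
- **That adjustment could have replaced the added recruitment.** Section 3.B says "We have increased enrollment to 200 in hopes to collect the number of completers we need to have significant power for statistical tests", and the Recruitment section ties the increase to lost and withdrawn participants. That is a shortage of completers, not excess outcome variance, so the two should not be traded against each other.
- **That omitting the urn factors distorts type I error.** If the factors were perfectly balanced and strongly prognostic, the unadjusted test would be somewhat conservative (about 4.0% at r = 0.3). The simulated urn gave 5.2%, so the unadjusted test is not at fault.

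**Conclusion.** The point holds as an inexpensive improvement, not as an error. The Phase 2 cocaine-use models omit a baseline that is collected on the outcome's own instrument, and the urn factors the plan chose to balance. For using days, pre-specified adjustment risks about 1 point of power if the covariates are unrelated to outcome and breaks even near r = 0.15. It gains about 1, 3 and 9 points at r = 0.2, 0.3 and 0.5. These figures rest on the plan's SD, effect and 144 completers, on an approximately normal analysis, and on an assumed r. The size of the benefit for dollars, relapse, latency and urine screens is not established. Fixing the covariates in advance has value whatever r proves to be, because it removes a choice that could otherwise be made after seeing results.

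**What to change.** Before unblinding, amend the Phase 2 part of the Data Analysis Plan:

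- **Using days:** replace ANOVA with ANCOVA on pre-study percent using days (three-month Timeline Follow-Back), gender and the $1000 urn factor.
- **Dollars:** ANCOVA on log(1 + pre-study dollars) and gender. State the outcome scale separately, since follow-up dollars will include zeros.
- **Relapse, latency and urine screens:** include pre-study use and the urn factors as fixed covariates in the logistic, Cox and mixed models. State that the resulting effects are conditional on them.
- **Supporting analyses:** report the unadjusted versions alongside.
- **Baseline comparisons:** state that they are descriptive and do not decide adjustment.

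The cue-session models need no change on this account. The cost is SAP wording, two or three degrees of freedom, and about 1 point of power for using days if the covariates prove uninformative. No new data are needed, because pre-study use is already collected for randomization. The R21 recorded both pre-study and follow-up use, so the sponsor could estimate r from it, though over a mean follow-up of only nine days.

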Participants will be informed that they will be expected to remain abstinent from cocaine and other drugs for the 72-hour period preceding their CTRC admission in order to minimize the impact of recent drug/alcohol use on cue reactivity and minimize any potential for interaction between propranolol and cocaine/alcohol. Participants will be asked to come in the day before CTRC admission for a urine drug screen. If an individual tests positive for drugs or alcohol on admission day and/or the day before admission day, their admission will be rescheduled and they will not be compensated for that visit. If participant shows signs of intoxication/withdrawal (elevated blood pressure, diaphoresis, etc.), they will also be rescheduled. Individuals who test positive for substance use will be provided transportation to their residence (taxi service) if friends or relatives are unable to meet this need.

Session Preparation

Upon arrival at the CTRC at approximately 9:00 am, the participant will give breath and urine samples to assess abstinence for alcohol and other substances (as well as pregnancy for females). Observed urine drug screens in which a research assistant will monitor urine collection may be done at all required abstinence visits to minimize tampering with urine specimen. If the abstinence assessment is negative (see above, if positive), they will remain at the CTRC lounge until 9:30, at which time study personnel will escort them to the cue reactivity laboratory. Over the course of the two-day inpatient stay at the CTRC, nicotine patches will be provided to smokers, thereby reducing the risk of nicotine withdrawal during the cue exposure procedure. During the next half hour, a blood pressure cuff will be placed on the participant's arm and leads/sensors will be affixed, as described below, for the purpose of collecting HR and SC data. Participants will also complete a few assessments at this time (e.g., State Trait Anxiety Inventory or STAI, BDI, CSSA described below). Since all of these tasks will be accomplished in 5-10 min, participants will remain seated quietly for the remaining 20 min period. This waiting period serves to acclimate the participant to the laboratory setting (our research group has found acclimation to produce more stable baseline measures in several laboratory studies).

Cocaine Cue Exposure (CCE): Stimuli and Procedures

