Follow-up Assessment Sessions: The goals of the follow-up visits are to determine if (a) the effects of post-retrieval propranolol on craving and cue reactivity to both familiar and novel cocaine cues are sustained over the 6-week follow-up, and (b) the post-retrieval propranolol treatment(s) impact cocaine use (variously measured) during follow-up. There will be a total of 18 visits scheduled over 6 weeks, with three visits occurring per week. All follow-up visits will begin with a drug/alcohol assessment. Briefly, participants will meet research staff at MUSC’s CTTC at approximately 9:00 a.m. on the pre-arranged day. At this time, a UDS and breathalyzer measurement will be obtained; cocaine, alcohol and other drug use status will be recorded. Next, research staff will perform a Timeline Follow-Back in order to ascertain the level of drug/alcohol use during the days since their last study visit. On follow-up visits that occur at the end of weeks 1, 3 and 6, participants will undergo a CCE session that is identical to the test session described above (test/follow-up CCE will follow drug/alcohol assessment). On these occasions, the cue exposures procedures will commence at approximately 10:30 a.m. to ensure that all study CCE sessions are being performed at approximately the same time of day (thereby serving to minimize the impact of circadian variation in sex and stress hormone levels on outcomes). Following CCE administration, the participant and staff will confirm the next appointment times and the appropriate level of compensation provided (see compensation plan below). At the end of each week, all appointments for the ensuing week will be scheduled. At the conclusion of the 6-week follow-up period, participants will be asked if they would like referrals for treatment

F. CCE Session Instruments and Related Measures

Self Report Measures

State-Trait Anxiety Inventory (STAI): The STAI is a 20-item self-report scale⁷² employing a Likert-scale format with four responses per item (1-4). Ten of the STAI items measure feelings of stress and anxiety, while the remaining ten items measure feelings of relaxation.

Cocaine Selective Severity Assessment (CSSA): The CSSA is an 18-item interview-based measure⁷³ of cocaine withdrawal symptom severity (e.g., lethargy, sleep disturbances, lethargy). It will be used to assess the association between withdrawal symptom severity and treatment response.

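### The hypothesis 3 models include follow-up cocaine use, a post-randomisation variable and the hypothesis 2 outcome, and no model without it is described

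*Combined protocol and SAP*

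**What the plan says.** Section 3.H, Data Analysis Plan, Phase 2, sets out hypothesis 3: participants given propranolol, compared with placebo, "will evidence less craving and cue reactivity to both familiar and novel cocaine cues presented during test/follow-up CCE sessions". Linear mixed effects models are to test it. Their whole description is: "The models will explore the effects of treatment, time, cocaine use status, and the interactions of the factors on the craving and physiologic responses" at the week 1, 3 and 6 sessions.

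The same section says under hypothesis 2 that propranolol-treated participants "will evidence less cocaine use during the 6-week follow up".

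Section 3.E (Follow-up Assessment Sessions) places the measurement of use at the follow-up visits, where "cocaine, alcohol and other drug use status will be recorded". On cue-session days this comes before the cues are shown.

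Section 3.H, Secondary Analysis, asks whether treatment affects ambient (non-cue-elicited) craving and adds: "The models will also test the effects of time and cocaine use status".

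For hypothesis 1, by contrast, Section 3.H (Phase 1) specifies a contrast of the two propranolol arms combined against placebo and lists no use term. It covers only the first test session.

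**The concern.** Hypothesis 3 asks whether the effect on craving and reactivity lasts over six weeks and extends to novel cues. It is a claim about randomised groups. A model that conditions on cocaine use during follow-up compares propranolol and placebo participants of the same use status, and those groups were formed after randomisation by something the trial itself expects treatment to change.

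Two things can then go wrong. Any part of the benefit that works through reduced use is removed from the treatment term. And if an unmeasured factor such as severity drives both use and craving, comparing users with users and non-users with non-users leaves the arms unbalanced on that factor.

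The interactions add a third problem. With treatment-by-use terms in the model, the treatment coefficient depends on coding. Under reference coding it is the effect in one use stratum only. The hypothesis names the groups to be compared but does not say how the comparison will be read from the model.

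**Working it through.** **Is use status a post-randomisation variable?** The analysis section does not define it. Section 1.C uses the same term for self-reported abstinence or use at follow-up in the R21, and Section 3.E records it at follow-up visits. A baseline meaning is implausible: all participants must currently be cocaine dependent (Section 3.L), and a positive screen leads to a rescheduled admission (Section 3.D).

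**Are the two links present?** Hypothesis 2 supplies the link from treatment to use. For use to craving, Section 3.D requires abstinence before admission in order to "minimize the impact of recent drug/alcohol use on cue reactivity", so the plan itself treats the link as real. It gives no size for it.

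**Figures in the plan.** There is no sample size or power statement for hypothesis 3, so there is no stated figure to reproduce.

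**Illustrative simulation.** 3,000,000 subjects, 2:1 propranolol to placebo (T = 1 for propranolol):

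- Severity S and noise e are independent N(0,1).
- Use = 1 if S + e exceeds a cut-off, set in each arm to give the stated use rate.
- Baseline craving = 40 + 10·S + noise (SD 18).
- Follow-up craving = 40 + 10·S + b·Use + d·T + noise (SD 18).
- The treatment coefficient comes from least squares adjusted for baseline, without and then with Use.

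From the documents: the R21 use rates (Section 1.C: "43% of the propranolol group and 35% of the placebo group participants reported using cocaine") and the 5.6-point difference in using days (Section 3.B, Phase 2), used only as a loose stand-in for a drop in use from 50% to 44.4%. All other inputs are assumptions.

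| d | b | Use, placebo / propranolol | Without Use (total) | With Use |
|---|---|---|---|---|
| -8 | 10 | 50% / 50% | -7.96 | -7.97 |
| -8 | 10 | 50% / 44.4% | -8.58 | -7.48 |
| -8 | 10 | 50% / 34% | -9.61 | -6.51 |
| -8 | 10 | 35% / 43% (R21) | -7.25 | -8.79 |
| -8 | 0 | 50% / 34% | -8.00 | -6.48 |
| -8 | -10 | 50% / 34% | -6.41 | -6.51 |
| 0 | 10 | 50% / 34% | -1.6 | +1.5 |
| 0 | 0 | 50% / 50% | 0.02 | 0.02 |
| 0 | 0 | 50% / 44.4% | 0.01 | 0.53 |
| 0 | 0 | 50% / 34% | 0.02 | 1.54 |
| 0 | 0 | 35% / 43% (R21) | 0.01 | -0.75 |

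**Reading the table.** The total effect is d + b × (use on propranolol − use on placebo):

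- 50% / 34%: -8 + 10 × (0.34 − 0.50) = -9.6
- R21 rates: -8 + 10 × (0.43 − 0.35) = -7.2

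The use-adjusted term hardly depends on b. It is d plus a selection shift from severity, about +1.5 at 50% / 34% and about -0.75 at the R21 rates. At 50% / 34% with b = 10 the gap of 3.1 points is therefore 1.6 (effect through use, removed) plus 1.5 (selection).

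As shares of the total:

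- 50% / 44.4%: (8.58 − 7.48)/8.58 = 13% lost
- 50% / 34%: (9.61 − 6.51)/9.61 = 32% lost
- R21 rates: (8.79 − 7.25)/7.25 = 21% overstated

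In the row with d = 0 and b = 10, where the only effect runs through reduced use, a real benefit of 1.6 points appears as harm of 1.5.

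**Interaction.** Adding treatment × Use (d = -8, b = 10, 50% / 34%) gives -6.61 in non-users, -6.38 in users and -6.52 with Use centred. None recovers -9.61. The interaction itself adds little here because the simulated direct effect is the same in both strata.

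**A different set-up.** With direct effect -10, use 60% / 40%, use adding 10 points and no baseline covariate, the total is about -12. The adjusted term is about -10 without a severity factor and about -8.4 with one (10 points per SD, correlation 0.5 with the liability to use).

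**Scale.** With the pooled craving SD of 22.3 (Section 3.B, Phase 1) and 96 versus 48 participants, SE = 22.3 × √(1/96 + 1/48) = 3.94 points. The gaps with d = -8 and b = 10 are 1.10/3.94 = 0.3 SE (44.4%), 1.54/3.94 = 0.4 SE (R21 rates) and 3.10/3.94 = 0.8 SE (34%). The null-case shifts (0.53, 1.54 and 0.75) are below half an SE.

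**The case against.** Four points can be made for the plan.

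- **The fault rests on silence.** The text speaks of models in the plural that will explore several factors, so a treatment-by-time model without use status is not ruled out. True, but none is described, and the sentence before makes these models the test of hypothesis 3.
- **Treatment-by-use is a question the protocol motivates.** Section 1.D suggests that repeated medicated retrievals may build resistance to craving that survives a brief lapse. This stands, and it is a good reason to keep the use-status models. It does not make them the randomised comparison. For ambient craving, the wording can also be read as adding a question rather than imposing a covariate, so the support there is weaker.
- **The figures depend on assumptions.** The 34% rate, the 10-point use effect and the severity link have no source in the documents. The null-case shift comes wholly from the severity factor: with severity set to 0 it vanishes, and at 5 points per SD the -0.75 becomes about -0.4. The R21 difference in use (p = .57) is not evidence that propranolol changes use. All of this stands. The figures show that the distortion can go either way, not what it will be.
- **The remedy goes further than the fault.** The baseline covariate is already planned (Section 3.H, Outcome Measures), and the urn factors are a separate modelling choice. Fair, but both are known before treatment and cost nothing to include.

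**Conclusion.** The concern holds. As described, the hypothesis 3 models condition on an outcome of treatment, and no analysis that estimates the total randomised effect at weeks 1, 3 and 6 is specified. The ambient-craving models have the same feature.

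The bias requires that propranolol changes use and that use is linked to craving, directly or through a shared cause. If use is the same in both arms, there is no shift. The two components can also cancel, as when use lowers craving by 10 points (-6.4 and -6.5 at 50% / 34%). Direction cannot be settled in advance: hypothesis 2 expects less use on propranolol, while the R21 rates ran the other way. In the scenarios with d = -8 and b = 10 where use differs, the gap is 1.1 to 3.1 points, or 0.3 to 0.8 of a simple two-group SE.

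The conclusion also rests on reading cocaine use status as a follow-up measure, which the documents support but do not state in the analysis section. The planned hypothesis 1 and 2 analyses do not adjust for use status and are not affected. This should be fixed, but it does not undermine the trial.

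**What to change.** In Section 3.H, state that hypothesis 3 and the ambient-craving question are tested in linear mixed models containing treatment, visit, treatment-by-visit, the first-retrieval baseline value and the two urn factors (gender; pre-study cocaine spend of $1000 or less versus more), without cocaine use status. Pre-specify the contrast of the two propranolol arms combined against placebo, as is done for hypothesis 1.

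Report models with use status and its interactions separately. Label them exploratory, define use status (source and time window), and state that they support no claim about the randomised treatment effect.

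The cost is one or two sentences in the analysis plan. No new data or procedures are needed, and no planned analysis is lost.
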